## 7.0 SCHEDULE OF EVALUATIONS

	Screening	Background Phase with Commercial SCS Device		Washout 24-48 hours	Investigational Phase with DISCSS™	
		Duration: 3-5 days			Duration: 3-4 Days	
	Day 0	Start of Commercial SCS Device Phase	End of Commercial SCS Device Phase		Start of DISCSS™ Device Phase	End of DISCSS™ Device Phase
	Visit 1 a	Visit 2 a	Visit 3		Visit 4	Visit 5
Informed Consent	X					
Inclusion/Exclusion Criteria	X b					
Eligibility Re-assessment					X b	
Demographics	X					
Physical Exam, Medical History and Conservative Therapy History	X					
Urine Pregnancy Test (females only)	X					
NRS Pain Assessment	X	X	X		X	X
Anatomical Pain Maps	X	X	X		X	X
Concomitant Medication Review	X	X	X		X	X
Patient Subjective Evaluation Questionnaire						X
Percutaneous Trial Lead Implantationc, Adjustment & Removal (under guided fluoroscopy)		X c, e			X c, e	X c, e
Radiographic Imaging of Implanted Percutaneous Trial Leads		X d			X d	X d

	Screening	Background Phase with Commercial SCS Device  Duration: 3-5 days		Washout 24-48 hours	Investigational Phase with DISCSS™  Duration: 3-4 Days	
	Day 0	Start of Commercial SCS Device Phase	End of Commercial SCS Device Phase		Start of DISCSS™ Device Phase	End of DISCSS™ Device Phase
	Visit 1 a	Visit 2 a	Visit 3		Visit 4	Visit 5
Device Use Initiation & Programming, and adjustment of External Pulse Generator (EPG) Settings		X			X	
EPG Removale			X			X
Commercial Device Complications Evaluation		X	X		X	
Adverse Event Review					X	X
Study Completion and Device Return						X

a Visit 1 and Visit 2 may be combined if eligibility is verified and all screening evaluations are completed prior to initiating Visit 2 activities.

b Eligibility criteria will be reviewed by the PI during Screening at Visit 1. PI will re-assess eligibility to continue participation in the Investigational Phase with the DISCSS™ SCS device at the start of Visit 4.

c Leads will be implanted percutaneously at Visit 2. At Visit 4 their positioning may be modified, if required. At Visit 5 they will be removed after the DISCSS™ EPG device is disconnected. Removal of percutaneous trial leads is not done under guided fluoroscopy.

d Radiographic imaging will be performed to document lead positions at Visit 2 once the leads have been implanted. At Visit 4 & 5 radiographic imaging will be performed to confirm that migration has not occurred.

e If applicable. Note: If the subject has existing permanent implanted leads in place, the permanent leads will be used, and the trial leads will not be implanted or removed.

## 8.0 INVESTIGATIONAL PRODUCT

### 8.1 Description of Investigational Product

The Meagan Medical, Inc. DISCSS™ System is comprised of the following components:

- Clinician programmer (Programmer)
- Patient remote (Remote)
- External feasibility neurostimulator (Stimulator)
- Patch cable

The stimulator applies electrical stimulation to the patient via a patch cable to implanted leads. The clinician programmer connects wirelessly to the stimulator to configure stimulation settings and provide stimulation to the patient. The patient remote connects wirelessly to the stimulator to activate stimulation, using only settings previously configured by the clinician programmer.

Stimulation consists of multiple sinusoidal waveforms driven to trial implanted lead electrodes positioned around the spinal column. Programmed stimulation parameters define the amplitude, frequency, phase, and duty cycle of the waveforms generated by the stimulator. Stimulation parameters also define the mapping of the generated waveforms to the lead set contacts.

A single sinusoidal waveform is referred to as a channel, which consists of both a positive and negative output. Channels are configured and activated in pairs,

referred to as clusters. The first channel of a cluster is driven at a base frequency and the second channel at a beat frequency.

## 8.2 Risk Analysis

Based on pre-clinical testing, Adverse Events that may be associated with the investigational DISCSS™ device include the following:

- Skin infection
- Spinal infection
- Allergic reaction
- Nerve damage
- Tissue inflammation
- Patient discomfort
- Electric shock
- Major tissue damage

Risks associated with the use of the investigational device and commercial device are expected to be comparable.

## 8.3 Methods to Minimize Risk

Adequate measures have been taken to minimize all of the above risks prior to initiation of a U.S. feasibility clinical study, including proper design specification and review, and preclinical testing.

The study Sponsor will provide appropriate training to each Investigator prior to each site's respective study initiation. Medical professionals will be trained on the selection criteria and protocol for the clinical study prior to their first use of the investigational device. The training will address topics such as the indications and contraindications for the use of the device, management of adverse events, and follow-up care.

Investigators will assess the possible presence of the risks associated with each device during the study treatment and at each follow-up visit by physical examination and participant interview as applicable.

## 8.4 Rationale for the Investigation

Although many of these risks are significant in nature, they are infrequent. The probability of incidence for any given event is extremely rare. Moreover, if use of the DISCSS™ system produces a successful result, it may reduce the participant's symptoms of pain and dysfunction. Based on these potential benefits, and the anticipated risks, Meagan Medical believes this study is justified.

## 8.5 Instructions for Use and Administration

Instructions for use of the DISCSS™ System are provided in the DISCSS™ Clinician Use Manual, which will be provided to each Principal Investigator during device use training, and retained in the site's regulatory files for reference during the study.

## 8.6 Packaging and Labeling

In accordance with federal regulations set forth in 21 CFR 812.5, the DISCSS™ System and User Manual will be labeled with the following statement:

'CAUTION – Investigational Device. Limited by Federal (or United States) law to investigational use.'

## 8.7 Investigational Product Accountability

The investigational device may only be used in the treatment of participants enrolled in the study. Investigators are responsible for the documented accountability for every investigational device. This includes maintaining the security of device inventory and keeping accurate records of device receipt, usage, and disposition. Each Investigator must adhere to the following:

- Each DISCSS™ trial system will be identified with a unique serial number and assigned to one patient on the trial. Following completion of Visit 5, each device will be returned to Meagan Medical.
- The investigational device may be only administered to patients under the Investigator's personal supervision and treatment, or under the supervision of an authorized sub-Investigator as designated in the Investigator's Agreement and the Delegation of Authority Log.
- The receipt, use, and disposition of the investigational device must be recorded in the Device Accountability Log.
- Complete and accurate accountability records must be kept, which document the receipt and transfer or return of all investigational devices for this study, including number of devices, catalogue part numbers, lot numbers, and names of all site personnel who received, used, transferred or returned the device(s) and associated dates.

The DISCSS™ trial system serial number will be linked to each patient's Subject ID in the EDC. The Subject Identification Number is the only Subject information entered into the DISCSS™ System during device calibration at Visit 4. Each DISCSS™ System used in this trial is designed to be used with one subject and returned to Meagan Medical upon study completion, unless the system is replaced for any reason during use as described in Section 8.9 Device Complications. In the event of device replacement, the serial number of the replacement device will be recorded on CRFs and entered into the EDC.

## **8.8     Return of Investigational DISCSS™ Device**

As described above, the DISCSS™ System will be returned to Meagan Medical after study completion for each subject for download of the device use log output as described in Appendix III: DISCSS™ Stimulator System Clinician Use Guide “Download Logs.” An electronic copy of the device use log output identified by device serial number and subject identification number will be transmitted to the Investigator site for storage with the Subject’s records. The device use logs will be uploaded to the database at Meagan Medical for analysis and storage.

## **8.9     Device Complications**

In the event of a device malfunction or complication, subjects will be advised to return to the clinic for evaluation as described in Section 6.7 Unscheduled Visits. The device complications and/or adverse events will be addressed clinically and per the procedures outlined in the protocol Study Procedures Section 6.0, Safety Reporting Section 10.0 and the DISCSS™ Stimulator System Clinician Use Guide. If indicated, the Investigator will adjust the settings on the DISCSS™ Stimulator System or, if necessary replace the DISCSS™ Stimulator System according to the Clinician Use Guide as outlined in Section 8.9. If the complication cannot be resolved, the subject will be discontinued from the study as described in Section 4.6.

All information regarding the adverse event, device malfunction or complication and replacement, as applicable will be captured in the medical records, Case Report Forms and entered into the clinical database. The malfunctioning device will be returned to Meagan Medical where the device use logs will be downloaded and analyzed.

## **9.0     CONCOMITANT MEDICATIONS/THERAPIES**

Study participants will be counseled to stop the use of the following medications throughout the duration of their study participation: warfarin, rivaroxaban, dabigatran, apixaban, edoxaban, enoxaparin, fondaparinux, and aspirin.

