## **4.0 STUDY ENROLLMENT AND WITHDRAWAL**

### **4.1 Inclusion Criteria**

In order to be eligible to participate in this study, an individual must meet all of the following criteria:

- a) Age greater than 21 years and less than 80 years
- b) Has a diagnosis of chronic neuropathic pain of trunk and limbs
- c) Is eligible for a spinal cord stimulation trial of a commercially available SCS trial system. Subjects will be evaluated at the end of the background Commercial SCS Device phase for complications and appropriateness to continue to the investigational phase with the DISCSS™ system. Complications from the background phase with the commercial SCS device may include, but are not limited to unusual pain or discomfort during the trial stimulation, local skin reactions or infection at the implant site.
- d) Has a Back Pain Score of minimum intensity 5.0 on a Numeric Rating Scale (NRS)
- e) Has an NRS Back Pain Score that is greater than both Leg Pain Scores
- f) Is not a candidate for revision surgery
- g) Has completed a minimum of 6 weeks of conservative therapy (physical therapy, anti-inflammatory medications, or similar therapies) with limited or no reduction in back pain
- h) Is willing to adhere to the warnings associated with the DISCSS™ system

- i) Is willing to halt and/or modify the use of all prescription and over-the-counter analgesics per the Investigator's direction during study participation
- j) Is capable of providing written informed consent
- k) Is able to comply with the requirements of study visits, follow-up phone visits and self-assessment questionnaires
- l) If existing permanent implanted leads are in place, the patient must be undergoing a paradigm shift in treatment (e.g. Conventional Sensory SCS to Sub-Perception SCS) that necessitates trialing of the new commercial SCS device.

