#### **4.2 Exclusion Criteria**

An individual who meets any of the following exclusion criteria at screening will be excluded from participation:

- a) Is a poor surgical candidate by determination of the Investigator
- b) Is unable to operate or understand the use of the commercial or investigational Spinal Cord Stimulator systems
- c) Has an active systemic infection
- d) Has exposure to shortwave, microwave or ultrasound diathermy at home or at work
- e) Has occupational exposure to high levels of non-ionizing radiation such as radio or cell phone transmission stations, facilities using radiofrequency heat sealers or induction heaters, or electric power infrastructure controlled environments
- f) Has an implanted cardiac system (e.g. pacemakers)
- g) Is currently participating in another clinical study
- h) Is currently pregnant or lactating, or not using adequate birth control
- i) Has any untreated major psychiatric comorbidity
- j) Has serious drug-related behavioral issues per Investigator's assessment
- k) Has a bleeding complication or coagulopathy
- l) Requires concurrent use of anticoagulant therapy such as heparin, warfarin, rivaroxaban, dabigatran, apixaban, edoxaban, enoxaparin, fondaparinux
- m) Is immunocompromised and at risk for infection
- n) Has insulin-dependent diabetes not controlled through diet and/or medication
- o) Has chronic pain related to malignancy
- p) Has used a commercially available SCS device within the last 14 days
- q) Is otherwise determined, based on the opinion of the Investigator to be an unsuitable candidate for this study

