### 5.0 STUDY SCHEMA

Screening	Background Phase Commerical SCS Device			Washout	Investigation Study Phase DISCSS™ SCS Device		
Day 0	Duration 3-5 days			Duration 1-2 days	Duration 3-4 days		
Visit 1	Visit 2		Visit 3		Visit 4		Visit 5

\*Please note that the Screening Visit (Visit 1, Day 0) may be combined with Visit 2 (Initiation of the Background Phase with Commercial SCS Device) upon Principal Investigator discretion and participant agreement. Combining Visit 1 and Visit 2 is contingent on successful verification of eligibility, completion of all screening evaluations, including meeting informed consent requirements.

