#### **6.4 Washout Period**

Participants will spend 24-48 hours undergoing a “washout period” between study phases.

During this period, they will be reminded not to increase the usual dosages of any of their prescribed medications, including pain medications. However, they may decrease their pain medications, if desired. All other prescribed medications (i.e., antihypertensives, hypoglycemics, cardiovascular medications, cardiopulmonary medications, membrane stabilizers, etc.) are to continue as usual.

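### Section 9.0 has participants counselled to stop anticoagulants and aspirin throughout the study, while Section 6.4 tells them to continue cardiovascular medications during washout; neither refers to the other

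*Protocol*

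**What the plan says.** Four parts of the protocol bear on this point.

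- **Section 9.0 (Concomitant Medications/Therapies):** "Study participants will be counseled to stop the use of the following medications throughout the duration of their study participation". The list that follows is "warfarin, rivaroxaban, dabigatran, apixaban, edoxaban, enoxaparin, fondaparinux, and aspirin". It is closed, and the section gives no visit for the counselling and no timing relative to any lead procedure.
- **Section 4.2, criterion (l):** excludes a patient who meets "Requires concurrent use of anticoagulant therapy such as heparin, warfarin, rivaroxaban, dabigatran, apixaban, edoxaban, enoxaparin, fondaparinux". Criterion (k) separately excludes a patient who "Has a bleeding complication or coagulopathy".
- **Section 6.4 (Washout Period):** participants must not raise the usual dose of any prescribed medication and may lower their pain medications. Then: "All other prescribed medications (i.e., antihypertensives, hypoglycemics, cardiovascular medications, cardiopulmonary medications, membrane stabilizers, etc.) are to continue as usual". Section 9.0 is not mentioned.
- **Section 5.0 (Study Schema):** the screening visit "may be combined with Visit 2 (Initiation of the Background Phase with Commercial SCS Device) upon Principal Investigator discretion and participant agreement". The condition is "Combining Visit 1 and Visit 2 is contingent on successful verification of eligibility, completion of all screening evaluations", together with informed consent. Section 6.1 and footnote a of Section 7.0 repeat the eligibility and screening conditions. None of the three mentions the Section 9.0 drugs.

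**The concern.** Two sentences about the same participants in the same 24-48 hours point in opposite directions for any Section 9.0 drug that is prescribed for a cardiovascular reason. Section 9.0 says stop; Section 6.4 says continue. The protocol does not say which takes precedence. With 5-7 centers, sites can follow different sentences and each claim to follow the protocol.

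The timing gives this practical weight. Visit 4 follows the washout directly, and if the leads have migrated they are repositioned under fluoroscopy at that visit. What is at stake is first the participant's safety around a lead procedure. Second is uniform conduct in the DISCSS phase, whose adverse events are the primary safety endpoint.

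Two smaller gaps add to it: the two drug lists do not match, and the combined-visit condition makes no link to the stop instruction.

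**Working it through.** The plan states no figure to reproduce on this point. The check compares the texts and counts days.

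**1. Section 9.0 against Section 6.4**

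| | Section 9.0 | Section 6.4 |
|---|---|---|
| Period | all of study participation | the 24-48 hours between Visits 3 and 4 |
| Drugs | seven anticoagulants and aspirin | all prescribed medications, with cardiovascular ones named among those that continue |
| Instruction | counselled to stop | continue as usual |
| Reference to the other section | none | none |

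The washout lies inside study participation, so both rows apply at once. Aspirin shows the conflict under either classification:

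- Taken as a prescribed cardiovascular drug, Section 6.4 says to continue it.
- Taken as a prescribed pain medication, Section 6.4 only forbids an increase and permits a decrease.

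Neither reading of Section 6.4 says stop.

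**2. Length of the conflict**

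From the durations in Section 5.0, Visit 2 to Visit 5 lasts:

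- Shortest: 3 + 1 + 3 = 7 days
- Longest: 5 + 2 + 4 = 11 days

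The washout is 1-2 of those days. Section 6.4 applies only there, so the one lead procedure that directly follows the conflict is the repositioning at Visit 4, which is done only if migration has occurred.

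**3. The two drug lists**

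| | Criterion 4.2(l) | Section 9.0 |
|---|---|---|
| Heparin | named | absent |
| Warfarin, rivaroxaban, dabigatran, apixaban, edoxaban, enoxaparin, fondaparinux | named | named |
| Aspirin | absent | named |
| Count | 1 + 7 = 8 | 7 + 1 = 8 |

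Seven drugs are common, and 7 + 1 + 1 = 9 are named in all. Because the Section 9.0 list is closed, heparin is literally outside the stop instruction.

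**4. Combined Visits 1 and 2**

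- Section 6.1 allows no study-specific procedure before consent, and consent is taken at Visit 1.
- Section 6.2 places lead implantation, where applicable, at Visit 2.
- If the visits are combined, the shortest interval from consent and counselling to implantation is 0 days.
- Aspirin is not named in any eligibility criterion. Criterion (l) excludes those who require an anticoagulant, not everyone who takes one. Eligibility can therefore be verified and screening completed while a Section 9.0 drug is still in use.
- Section 6.1 takes a medication history and Section 6.2 a concomitant medication review, but neither ties the result to Section 9.0 or lists the counselling.

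**5. Link to the primary safety endpoint**

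Section 3.2 counts adverse events arising from the DISCSS treatment phase. Section 3.1 says that complications data from the background phase are not analysed for the endpoints. Implantation at Visit 2 is in the background phase; repositioning at Visit 4 and removal at Visit 5 belong to the DISCSS phase.

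**The case against.** The strongest reply is that Section 9.0 is specific and covers the whole study, so a listed drug should already be stopped before washout and continuing as usual would mean continuing whatever remains. Patients who require anticoagulants are excluded, and aspirin used as an analgesic comes under inclusion criterion (i), by which the participant "Is willing to halt and/or modify the use of all prescription and over-the-counter analgesics" as the Investigator directs. On this view only a cross-reference is missing. That is a sensible reading, but the protocol does not state it. Prescribed cardiovascular aspirin remains under both sentences, and Section 6.4 names cardiovascular medications explicitly.

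The reply stands against several stronger readings that a reader might infer:

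- **That criterion 4.2(l) and Section 9.0 contradict each other.** They do not strictly do so. The criterion excludes those who require an anticoagulant; Section 9.0 can apply to those who are able to stop. The criterion's list is open, and it concerns anticoagulants, so the absence of aspirin there is no error. What remains is the absence of heparin from the closed list and an undefined boundary between requiring a drug and being counselled to stop it.
- **That every lead procedure falls under opposite instructions.** Section 6.4 does not apply before Visit 2, and Visit 5 comes 3-4 days after washout ends. Participants with existing permanent leads have no trial leads implanted or removed.
- **That same-day counselling and implantation is planned.** It is only permitted. Investigator discretion, exclusion criteria (a), (k), (l) and (q), the medication reviews and the lead manufacturer's instructions all give some protection.
- **That a bleed at Visit 2 would distort the primary safety endpoint.** Section 3.1 keeps the background phase out of the endpoint analysis.
- **That the rule cannot be used at all.** The criteria can be applied at screening, and Section 9.0 is clear when read alone.

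**Conclusion.** The point holds as an inconsistency between instructions that concern participant safety. During the 1-2 day washout, a Section 9.0 drug prescribed for a cardiovascular reason is subject both to a stop instruction and to a continue instruction, just before a possible lead procedure at Visit 4. Two gaps accompany it. Heparin is named in the exclusion but not in the stop list, and the combined-visit condition allows counselling and implantation 0 days apart without mentioning the stop instruction.

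This rests on two assumptions: that Section 6.4's cardiovascular medications include prescribed aspirin or anticoagulants, and that study participation in Section 9.0 includes the washout. The plain wording supports both.

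The size is limited. Only the Visit 4 and later procedures bear on the primary safety endpoint. The documents give no bleeding rate and do not say how many participants will be taking a listed drug, so no effect on event counts can be calculated. No statistical figure in the plan changes. The point still merits correction before enrollment proceeds, because these are instructions to sites and participants that an analysis plan would not settle.

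**What to change.** The sponsor and investigators should:

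1. Reconcile Sections 4.2(l), 6.4 and 9.0 into one consistent instruction, with each section referring to it. This includes settling whether heparin belongs in Section 9.0 and how a patient who requires a drug is distinguished from one who is counselled to stop it.
2. Make the condition for combining Visits 1 and 2 in Sections 5.0 and 6.1, and footnote a of Section 7.0, consistent with that instruction.

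Which drugs are listed, which of the two instructions governs during washout and when drugs are stopped are clinical decisions for them; this review takes no position on any of these.

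The cost is protocol wording, with the IRB approval of an amendment that Section 13.1 calls for. The reconciliation itself requires no change to the sample size of 30, the endpoints or the descriptive analysis.
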